9.2 Responsibility for Analyses

The statistical analysis of the data obtained from this study will be conducted by, or under the direct auspices of, the Clinical Biostatistics Department in collaboration with the Quantitative Pharmacology and Pharmacometrics Department and Translational Pharmacology Department of the Sponsor.

If, after the study has begun, changes are made to the statistical analysis plan stated below, then these deviations to the plan will be listed, along with an explanation as to why they occurred, in the Clinical Study Report.

9.3 Hypotheses/Estimation

Objectives of the study are stated in the Section 3.

9.4 Analysis Endpoints

Primary Endpoints

1. AEs

Secondary Endpoints

1. Pharmacokinetics: Plasma AUC0-inf, AUC0-last, AUC0-168, Cmax, C168, Tmax, Tlast, t1/2, CL and Vz
2. Pharmacodynamics: aPTT (fold change from baseline)

Exploratory Endpoints

1. Factor XI activity (fold change from baseline)
2. Prothrombin time (fold change from baseline)
3. Time to hemostasis
4. ADA

For change from baseline, the baseline is defined as the panel-specific pre-dose value.

9.5 Analysis Populations

The following populations are defined for the analysis and reporting of data. All participants will be reported, and their data analyzed, according to the treatment(s) they actually received.

All Participants as Treated (APaT): The All Participants as Treated Population consists of all participants who received at least one dose of treatment. This population will be used for assessments of safety.

Per-Protocol (PP): The Per-Protocol Population consists of the set of data generated by the subset of participants who comply with the protocol sufficiently to ensure that these data will be likely to exhibit the effects of treatment, according to the underlying scientific model. Compliance covers such considerations as exposure to treatment, availability of measurements and absence of major protocol deviations. Major protocol deviations will be identified to the extent possible prior to unblinding by individuals responsible for data collection, and its analysis and interpretation. Any participants or data values excluded from analysis will be identified, along with their reason for exclusion, in the CSR. At the end of the study, all participants who are compliant with the study procedure as aforementioned and have available data from at least one treatment will be included in the Per-Protocol dataset. This population will be used for the PK and PD analyses.

9.6 Statistical Methods

Safety

AEs will be tabulated by treatment. Summary statistics and plots will be generated for raw laboratory safety tests, ECGs, and vital sign as well as for change from baseline, as deemed clinically appropriate. Depending on the safety parameter, the difference from baseline will either be computed on the original scale (raw change from baseline) or on the log scale and back-transformed for reporting (percent change from baseline).

Pharmacokinetics

Values will be listed for each PK parameter and appropriate non-model based descriptive statistics will be provided: N (number of participants with non-missing data), arithmetic mean, standard deviation, arithmetic percent CV (calculated as 100 x standard

deviation/ arithmetic mean), median, minimum, maximum, geometric mean and geometric percent CV (calculated as $100 \times \sqrt{\exp(s^2) - 1}$, where s^2 is the observed variance on the natural log-scale).

Pharmacodynamics

Individual aPTT fold-change from baseline values will be natural log-transformed and evaluated with a linear mixed effect model containing fixed effects for treatment, time and treatment by time interaction and random effect for participant. Least squares means and 95% confidence intervals for each treatment, and for the between-treatment difference (MK-2060-placebo) and 90% CI at each dose level, will be obtained by time. These estimates will be back-transformed to obtain GM aPTT fold-change from baseline by treatment time and the GMR (MK-2060 fold-change from baseline/placebo fold-change from baseline) by dose and time.

The proportion of participants with a fold-increase in aPTT 168 hours after a single dose of at least **CC** will be tabulated.

Summary statistics will be provided for PD endpoints by time.

The relationship between plasma concentrations and aPTT, FXI activity, and PT may be explored graphically.

ADA

The number of participants with positive / negative antibody drug response to antibodies to MK-2060 will be summarized. Frequency counts for the maximum antibody titer for participants classified as positive will also be reported.

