Assessment of Time to Hemostasis	X	X				X					X		X			X				
Height	X																			
Weight	X																X			
Resting Vital Signs (BP, PR and RR)	X	X	X ----- X						X	X	X	X	X	X			X	X	On Day 1~2, BP, PR and RR will be measured at predose, 15 min, 30 min, and 1, 2, 3.5, 12 and 24 hours postdose. Predose PR and BP will be triplicate measurements obtained at least 1 to 2 minutes apart within 3 hours of starting dialysis session.	
Resting Vital Signs (body temperature)	X	X	X		X	X			X	X		X	X	X			X	X		
12-lead ECG	X		X			X			X	X		X						X		
Hematology and Chemistry	X	X	X						X	X		X	X	X	X	X	X	X		
aPTT and PT	X			X			X		X		X	X	X	X	X	X	X			
CCI			X																	

	Screening		Intervention													Post-study	Phone Call	Note			
	1	2	3				4	5	6	7	8	9	10	11	12	13					
Visit Number	1	2																			
Scheduled Day	Scr1	Scr2	1~2				3	5	8	12	15	22	29	60	90	120	150	164			
Scheduled Hour (0= Initiation of Administration)			Pre dose	0	1	3.5	8	12	24	48	52	96	168								
Window (Day)												+1		±1	±2	±2	±3	±5	±5	±7	Window of Screening: See Section 8.11.1
Hemoccult Test	X									X		X	X	X	X	X					
HIV, hepatitis B and C screen	X																				
Saliva Drug Screen	X																				
FSH	X	X																	As needed.		
AE/SAE review	X		-----													X					
Pharmacokinetics																					
Blood for Plasma MK-2060 Assay			X		X		X	X	X	X	X	X	X	X	X	X	X	X	Days 8, 29 and 120: two draws for a pre- dialysis and a post- dialysis sample.		
Blood for plasma ADA			X											X	X	X	X	X			
Pharmacodynamics																					
Blood for aPTT/PT/FXI activity			X		X		X	X	X	X	X	X	X	X	X	X	X	X	Days 8, 29 and 120: two draws for a pre- dialysis and a post- dialysis sample.		
Biomarkers																					
Blood for Genetic Analysis			X																See Section 8.8.1.		

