4.2 Scientific Rationale for Study Design

MK-2060 is being developed for the prevention of thrombotic vascular events in ESRD patients, thus the objectives of this study are to evaluate safety, tolerability, PK, and PD of MK-2060 after a single dose IV administration in Japanese patient population [older participants with ESRD on dialysis (participants assigned male sex at birth or WONCBP

between the age of 50 to 80 years)]. Approximately up to 16 participants with ESRD on dialysis who meet study eligibility criteria may be enrolled in this study.

Dialysis modality in this study includes HD and HDF. The Japanese patients treated by HDF have been increasing in number rapidly since 2012. HD and HDF accounted for 49.3% and 47.1% of all dialysis patients, respectively in 2020 [JSDT Renal Data Registry 2020]. Therefore, this study will enroll both HD and HDF participants. Since only HD participants were enrolled in MK-2060-004 (Phase 1 study in non-Japanese participants), this study will mainly enroll HD participants and a minimum of approximately [REDACTED] HDF participants will be enrolled. [REDACTED]

[REDACTED] is not removed by both HD and HDF, it is anticipated that there is no PK difference between HD and HDF patients.

The mean age of prevalent dialysis patients in Japan was 69.40 years, indicating a gradual annual increase. The age group of 70 to 74 had the highest percentage both in males and females [JSDT Renal Data Registry 2020]. The mean age of HD and HDF patients was 70.00 years and 67.21 years, respectively. The mean dialysis vintage of HD patient was 6.99 years and 50.7% was less than 5 years of dialysis vintage. On the other hand, the mean dialysis vintage of HDF patient was 8.44 years and 40.9% was less than 5 years of dialysis vintage. HDF is applied to relatively young patients with a longer dialysis vintage than HD in 2018 [JSDT Renal Data Registry 2018]. Therefore, this study is being conducted in older participants ages from 50 years to 80 years.

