In the Part 1 of MK-2060-004, the exposure (AUC0-inf and Cmax) after single IV dose at 8 mg MK-2060 in non-Japanese ESRD participants on HD is comparable to non-Japanese healthy participants (MK-2060-001) while the exposure after single IV dose at 20 mg and 40 mg in non-Japanese ESRD participants on HD are slightly lower than that in non-Japanese healthy participants due to higher clearance. The terminal t1/2 ranged from ~14 days for MK-2060 8 mg to ~21 days for MK-2060 40 mg in non-Japanese ESRD participants on HD [REDACTED]. PK samples were also collected pre- and post-dialysis, with the post-dialysis PK concentration approximately [REDACTED] higher than pre-dialysis indicating that MK-2060 is not cleared via dialysis and the reduction in volume due to dialysis slightly increases the MK-2060 concentration. Based on single dose PK and aPTT or FXIa activity data, [REDACTED].

The PK and aPTT or FXI activity (relative of baseline) data from MK-2060-001 and following single IV doses from MK-2060-004 suggests a comparable but [REDACTED] for participants with ESRD and healthy participants.

It is also not anticipated that race significantly alter the PK and PD of MK 2060. As mAbs are primarily eliminated via catabolism, there is expected to be no ethnic differences of the clearance between Japanese and non-Japanese participants. Since the PK and PD values were correlated [REDACTED] in non-Japanese, PD responses in Japanese participants are also expected to be similar to that in non-Japanese participants. The impact of race on MK-2060 PK and PD will be further assessed by conducting single dose study in Japanese healthy participants (MK-2060-013).

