8.11.5 Critical Procedures Based on Study Objectives: Timing of Procedure

For this study, the blood sample for MK-2060 is the critical procedure.

At any postdose time point, the blood sample for MK-2060 needs to be collected as close to the exact time point as possible. All other procedures should be completed as close to the prescribed/scheduled time as possible. Study procedures can be performed before or after the prescribed/scheduled time.

The order of priority can be changed during the study with joint agreement of the investigator and the Sponsor Clinical Director.

Any nonscheduled procedures required for urgent evaluation of safety concerns take precedence over all routine scheduled procedures.

The following variance in procedure collection times will be permitted.

- Blood collection for PK, PD, ADA, laboratory safety tests, including aPTT/PT, and genetic analysis as outlined in [Table 6](#).

Table 6 Blood Collection Windows

Collection Time	Collection Window
Predose	Within 3 hrs prior to the initiation of dialysis
1 hr	Immediately prior to the end of IV infusion (i.e. no more than 5 min before anticipated time of the end of IV infusion)
12 hrs	±15 min
24 hrs	±1 hr
48 hrs	± 1 hr and prior to the initiation of dialysis
52 hrs	Post dialysis
96 hrs	± 2 hrs and prior to the initiation of dialysis. If this prescribed time is not dialysis day, +1 day and prior to the initiation of dialysis.
168 hrs	± 2 hrs and prior to the initiation of dialysis. Blood samples for PK and PD will be also collected at post dialysis.
Day 12	±1 day and within 12 hrs prior to the initiation of dialysis
Days 15 and 22	±2 days and within 12 hrs prior to the initiation of dialysis
Day 29	±3 days and within 12 hrs prior to the initiation of dialysis. Blood samples for PK and PD will be also collected at post dialysis.
Days 60 and 90	±5 days and within 12 hrs prior to the initiation of dialysis
Day 120	±7 days and within 12 hrs prior to the initiation of dialysis. Blood samples for PK and PD will be also collected at post dialysis.
Day 150	±7 days and within 12 hrs prior to the initiation of dialysis

- Safety evaluations for PE, systemic infusion reaction assessment, VS and 12-lead ECG as outlined in [Table 7](#).

Table 7 Safety Evaluations Windows

Evaluation Time	Evaluation Window
Predose	Within 3 hrs prior to the initiation of dialysis
15 and 30 min	±15 min
1 and 2 hrs	
3.5 hrs	±15 min
8 hrs	±15 min
12 hrs	±30 min
24 hrs	±1 hr

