9 STATISTICAL ANALYSIS PLAN

9.1 Statistical Analysis Plan Summary

This section contains a summary of the statistical analyses for this trial. Full detail can be found in the subsequent sections.

Safety

AEs will be tabulated by treatment group. Summary statistics and plots will be generated for raw laboratory safety tests, ECGs, and vital sign as well as for change from baseline, as deemed clinically appropriate. Depending on the safety parameter, the difference from baseline will either be computed on the original scale (raw change from baseline) or on the log scale and back-transformed for reporting (percent change from baseline).

Pharmacokinetics

Individual values will be listed for each PK parameter and appropriate non-model based descriptive statistics will be provided: N (number of participants with non-missing data), arithmetic mean, standard deviation, arithmetic percent CV (calculated as $100 \times$ standard deviation/ arithmetic mean), median, minimum, maximum, geometric mean and geometric percent CV (calculated as $100 \times \text{sqrt}(\text{exp}(s^2)-1)$, where s^2 is the observed variance on the natural log-scale).

Pharmacodynamics

Individual aPTT fold-change from baseline values will be natural log-transformed and evaluated with a linear mixed effect model containing fixed effects for treatment, time and treatment by time interaction and random effect for participant. Least squares means and 95% confidence intervals for each treatment, and for the between-treatment difference (MK-2060-placebo) and 90% CI at each dose level, will be obtained by time. These estimates will be back-transformed to obtain GM aPTT fold-change from baseline by treatment time and the GMR (MK-2060 fold-change from baseline/placebo fold-change from baseline) by dose and time.

The proportion of participants with a fold-increase in aPTT 168 hours after a single dose of at least 1.5 will be tabulated.

Sample Size and Power Calculations

The total participants of approximately 16 (MK-2060=approximately ~~CC~~ placebo=approximately ~~CC~~) is considered to be adequate to address the primary objective of the study.

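### Does Section 9 need a post-/pre-dialysis MK-2060 ratio and a PK display by HD and HDF?

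*Combined protocol and SAP*

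**What the plan says.** Section 9.6 covers PK in one sentence: "Values will be listed for each PK parameter and appropriate non-model based descriptive statistics will be provided". The summary in 9.1 is nearly the same: "Individual values will be listed for each PK parameter and appropriate non-model based descriptive statistics will be provided". The endpoints in 9.4 are ten non-compartmental parameters. A post/pre concentration ratio is not among them, and Section 9 does not mention dialysis, HD or HDF. The redactions visible there cover arm sizes and an aPTT threshold, so they do not appear to hide such an analysis.

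The sampling is more detailed. The note in 1.3 reads "Days 8, 29 and 120: two draws for a pre- dialysis and a post- dialysis sample", and Table 6 in 8.11.5 repeats for 168 h, Day 29 and Day 120: "Blood samples for PK and PD will be also collected at post dialysis". Table 6 also places the 48 h draw before dialysis and the 52 h draw after it.

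Section 4.2 explains the mix of modalities. It puts HDF at 47.1% of Japanese dialysis patients in 2020 and concludes: "Therefore, this study will enroll both HD and HDF participants". It notes that "only HD participants were enrolled in MK-2060-004" and, after a redacted stretch, states that the drug "is not removed by both HD and HDF, it is anticipated that there is no PK difference between HD and HDF patients". On the pre/post samples of that HD study it reports a higher post-dialysis concentration, "indicating that MK-2060 is not cleared via dialysis and the reduction in volume due to dialysis slightly increases the MK-2060 concentration". The footnote to Table 3 (6.3.1) asks for at least about 8 HDF participants among up to 16. Section 6.3.2 rules out stratification.

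**The concern.** The protocol collects the kind of evidence that was used in HD to infer that dialysis does not remove the drug. It now collects it in HDF as well, where the visible text gives no clinical data, and then plans no display of it. Section 2.1 says the results will help choose doses for Japanese participants, and nearly half of Japanese dialysis patients are on HDF. If HDF removed a little drug at each session, the loss would compound over three sessions a week and lower AUC0-inf in that subgroup. Pooled with HD in one summary, a modest reduction could pass as ordinary spread between participants.

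**Working it through.** **1. Number of pairs.** Table 6 and the schedule give 16 PK times: predose, 1, 12, 24, 48, 52, 96 and 168 h, and Days 12, 15, 22, 29, 60, 90, 120 and 150. Adding the three extra post-dialysis draws gives 16 + 3 = 19. Appendix 8 gives 8 (PK with ADA) + 11 (PK only) = 19, so the count agrees. Without 52 h it would be 18, so 52 h is a PK draw. The pairs are 48/52 h and Days 8, 29 and 120: 4 pairs, or 8/19 = 42% of PK draws.

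**2. What the planned listing would show.** Inputs: t1/2 of 14 to 21 days (4.2) and three sessions a week (5.1, criterion 2). The net fractional loss per session, L, is assumed. In a one-compartment model

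k = ln 2 / t1/2; k_eff = k + (3/7) × (−ln(1 − L)); AUC0-inf ratio = k / k_eff.

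For t1/2 = 14 days and L = 5%: k = 0.0495, added rate = (3/7) × 0.0513 = 0.0220, k_eff = 0.0715, new t1/2 = 9.7 days, ratio = 0.69.

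| L | t1/2 14 d: new t1/2, AUC ratio | t1/2 21 d: new t1/2, AUC ratio |
|---|---|---|
| 2% | 11.9 d, 0.85 | 16.6 d, 0.79 |
| 5% | 9.7 d, 0.69 | 12.6 d, 0.60 |
| 10% | 7.3 d, 0.52 | 8.9 d, 0.42 |
| 20% | 4.8 d, 0.34 | 5.4 d, 0.26 |

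Losses of 10-20% would stand out among individual values without any split.

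**3. What a split of AUC by modality would add.** The arm sizes are redacted, so 4+4 and 6+6 HDF and HD participants on MK-2060 are assumed. With CV 30% (assumed), the log SD is √ln(1.09) = 0.294. The 90% interval factor is exp(t(0.95, n1+n2−2) × SD × √(1/n1 + 1/n2)):

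- 4+4: exp(1.943 × 0.294 × 0.707) = 1.50
- 6+6: exp(1.812 × 0.294 × 0.577) = 1.36

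A 2% loss is a factor of 1/0.85 to 1/0.79 = 1.18 to 1.27, inside both. A 5% loss is 1/0.69 to 1/0.60 = 1.45 to 1.67, near or beyond them. The split helps only around 5%.

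**4. What a post/pre ratio would add.** Fluid removal raises the post-dialysis concentration (4.2), so the reference is the HD ratio, not 1, and the interval must be two-sample. With an assumed log-ratio SD of 0.10 to 0.20 and the same formula:

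- 4+4: 0.87-1.15 to 0.76-1.32
- 6+6: 0.90-1.11 to 0.81-1.23

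One occasion cannot exclude a loss of a few percent.

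**5. Limits of the ratio itself.** On Days 29 and 120 the pre-dialysis draw may be up to 12 h before dialysis (Table 6). With an assumed 4 h session the gap is 16 h, and elimination alone lowers the post value by 1 − 2^(−(16/24)/t1/2) = 3.2% (14 d) to 2.2% (21 d). That is as large as much of the loss in question. By Day 120, 2^(−119/14) to 2^(−119/21), or 0.3% to 2%, of the drug remains, so that pair says little. The extra post-dialysis draws on Days 8, 29 and 120 are for PK and PD only, and the schedule shows weight only twice in the whole study. Nothing is scheduled with each pair to separate removal from fluid loss.

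**6. Objectives.** Section 3 and 9.4 contain no dialysis-clearance or modality comparison, and 9.8 states that there are no hypotheses. Section 4.2 gives prevalence, not comparison, as the reason for enrolling HDF.

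**The case for a change.** The best case for a change is that it costs almost nothing: one small table and one listing column from samples already planned. The question comes from the protocol's own rationale. Writing the display down now would avoid choosing it after the results are seen. Section 8.6 leaves it to the Sponsor which plasma samples are assayed, so nothing commits anyone to report the pairs. A within-participant ratio is also free of between-participant spread.

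The facts in this stand, and a team that wants the table may add it as descriptive output. What does not stand is the step from useful to needed. Section 9 prescribes no listing columns, so a listing that omits modality is an inference from silence. HD or HDF status is fixed by eligibility and can be joined to any output. The same sponsor compared pre- and post-dialysis concentrations in MK-2060-004 and knows how to do it. The freedom from between-participant spread is partly offset by fluid loss, sampling times and the need for an HD reference. In a study of about 16 participants without hypotheses, there is little at risk from choosing a descriptive display late.

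**Conclusion.** No change to the plan is needed. The silence is a gap in exploratory reporting that analysts can fill sensibly from data the protocol already provides. The safety, PK and aPTT objectives are unaffected, and every PK endpoint in 9.4 is covered by the planned listing and summaries.

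The possible benefit is confined to net losses of around 5% per session. Larger ones show in the planned listing, and losses near 2% are beyond either display at 4+4 or 6+6. This rests on the one-compartment model, the 14-21 day half-lives carried over from non-Japanese HD patients, and assumed values for CV, log-ratio SD, session length and group sizes. Exactly 8 HDF among 16 with 12 on MK-2060 (assumed) would put 4 to 8 HDF participants on active drug, most likely 6 (43%). Part of the reasoning for HDF in 4.2 is redacted, so its strength cannot be judged here.

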9.7 Interim Analyses

No formal interim analysis is planned.

9.8 Multiplicity

Since there are no pre-specified hypotheses, no adjustments for multiplicity are needed.

9.9 Sample Size and Power Calculations

The total participants of approximately 16 (MK-2060=approximately **CC**, placebo=approximately **CC**) is considered to be adequate to address the primary objective of the study.

10 SUPPORTING DOCUMENTATION AND OPERATIONAL CONSIDERATIONS

10.1 Appendix 1: Regulatory, Ethical, and Study Oversight Considerations

10.1.1 Code of Conduct for Clinical Trials

Merck Sharp & Dohme LLC, Rahway, NJ, USA (MSD)

Code of Conduct for Interventional Clinical Trials

I. Introduction

A. Purpose

Merck Sharp & Dohme LLC, Rahway, NJ, USA (MSD), through its subsidiaries, conducts clinical trials worldwide to evaluate the safety and effectiveness of our products. As such, we are committed to designing, planning, conducting, analyzing, and reporting these trials in compliance with the highest ethical and scientific standards. Protection of participants in clinical trials is the overriding concern in the design and conduct of clinical trials. In all cases, MSD clinical trials will be conducted in compliance with MSD's global standards, local and/or national regulations (including all applicable data protection laws and regulations), and International Council for Harmonisation Good Clinical Practice (ICH-GCP) E6 and ICH General Considerations for Clinical Studies E8, and in accordance with the ethical principles that have their origin in the Declaration of Helsinki.

B. Scope

Highest ethical and scientific standards shall be endorsed for all clinical interventional investigations sponsored by MSD irrespective of the party (parties) employed for their execution (e.g., contract research organizations, collaborative research efforts). This Code is not intended to apply to trials that are observational in nature, or which are retrospective. Further, this Code does not apply to investigator-initiated trials, which are not under the full control of MSD.

II. Scientific Issues

A. Trial Conduct

1. Trial Design

Except for pilot or estimation trials, clinical trial protocols will be hypothesis-driven to assess safety, efficacy and/or pharmacokinetic or pharmacodynamic indices of MSD or comparator products. Alternatively, MSD may conduct outcomes research trials, trials to assess or validate various endpoint measures, or trials to determine patient preferences, etc.

The design (i.e., participant population, duration, statistical power) must be adequate to address the specific purpose of the trial and shall respect the data protection rights of all participants, trial site staff and, where applicable, third parties. Input may be considered from a broad range of stakeholders, including patient advocacy groups/patients representing the trial population, caregivers, and healthcare providers to ensure operational feasibility. Trial design also includes proactive identification of critical to quality factors utilizing a risk-based approach. Plans are then developed to assess and mitigate risks to those factors as appropriate during the trial. All trial protocols are and will be assessed for the need and capability to enroll underrepresented groups. Participants must meet protocol entry criteria to be enrolled in the trial.

2. Site Selection

MSD's clinical trials are conducted globally in many different countries and in diverse populations, including people of varying age, race, ethnicity, gender, and accounting for other potential disease related factors. MSD selects investigative sites based on medical expertise, access to appropriate participants, adequacy of facilities and staff, previous performance in clinical trials, as well as budgetary considerations. Prior to trial initiation,

sites are evaluated by MSD personnel (or individuals acting on behalf of MSD) to assess the ability to successfully conduct the trial. Individuals involved in trial conduct receive training commensurate with their role prior to their becoming involved in the trial.

Where appropriate, and in accordance with regulatory authority guidance, MSD will make concerted efforts to raise awareness of clinical trial opportunities in various communities. MSD will seek to engage underrepresented groups and those disproportionately impacted by the disease under study. MSD will support clinical trial investigators to enroll underrepresented groups and expand access to those who will ultimately use the products under investigation.

3. Site Monitoring/Scientific Integrity

Investigative trial sites are monitored to assess compliance with the trial protocol and Good Clinical Practice (GCP). MSD reviews clinical data for accuracy, completeness, and consistency. Data are verified versus source documentation according to standard operating procedures. Per MSD policies and procedures, if potential fraud, scientific/research misconduct, privacy incidents/breaches or Clinical Trial-related Significant Quality Issues are reported, such matters are investigated. When necessary, appropriate corrective and/or preventative actions are defined and regulatory authorities and/or ethics review committees are notified.

B. Publication and Authorship

Regardless of trial outcome, MSD commits to publish the primary and secondary results of its registered trials of marketed products in which treatment is assigned, according to the pre-specified plans for data analysis. To the extent scientifically appropriate, MSD seeks to publish the results of other analyses it conducts that are important to patients, physicians, and payers. Some early phase or pilot trials are intended to be hypothesis-generating rather than hypothesis testing; in such cases, publication of results may not be appropriate since the trial may be underpowered and the analyses complicated by statistical issues such as multiplicity.

MSD's policy on authorship is consistent with the recommendations published by the International Committee of Medical Journal Editors (ICMJE). In summary, authorship should reflect significant contribution to the design and conduct of the trial, performance or interpretation of the analysis, and/or writing of the manuscript. All named authors must be able to defend the trial results and conclusions. MSD funding of a trial will be acknowledged in publications.

III. Participant Protection

A. Regulatory Authority and Ethics Committee Review (Institutional Review Board [IRB]/Independent Ethics Committee [IEC])

All protocols and protocol amendments will be submitted by MSD for regulatory authority acceptance/authorization prior to implementation of the trial or amendment, in compliance with local and/or national regulations.

The protocol, protocol amendment(s), informed consent form, investigator's brochure, and other relevant trial documents must be reviewed and approved by an IRB/IEC before being implemented at each site, in compliance with local and/or national regulations and ICH Guidelines. Changes to the protocol that are required urgently to eliminate an immediate hazard and to protect participant safety may be enacted in anticipation of ethics committee approval. MSD will inform regulatory authorities of such new measures to protect participant safety, in compliance with local and/or national regulations.

B. Safety

The guiding principle in decision-making in clinical trials is that participant welfare is of primary importance. Potential participants will be informed of the risks and benefits of, as well as alternatives to, trial participation. At a minimum, trial designs will take into account the local standard of care.

All participation in MSD clinical trials is voluntary. Participants enter the trial only after informed consent is obtained. Trial designs include procedures and systems for the identification, monitoring and reporting of safety

concerns. Participants may withdraw from an MSD trial at any time, without any influence on their access to, or receipt of, medical care that may otherwise be available to them.

During trial planning, the need for an independent Data Monitoring Committee (DMC) is assessed. DMC review of data accumulated during the conduct of the trial is integral to the well-being of trial participants.

C. Confidentiality

MSD is committed to safeguarding participant confidentiality, to the greatest extent possible, as well as all applicable data protection rights. Unless required by law, only the investigator, Sponsor (or individuals acting on behalf of MSD), ethics committee, and/or regulatory authorities will have access to confidential medical records that might identify the participant by name.

D. Genomic Research

Genomic research will only be conducted in accordance with a protocol and informed consent authorized by an ethics committee.

E. Trial Results

At the time of providing informed consent and in accordance with local laws and regulations, participants should be informed about the plans for availability of trial results.

IV. Financial Considerations

A. Payments to Investigators

Clinical trials are time- and labor-intensive. It is MSD's policy to compensate investigators (or the sponsoring institution) in a fair manner for the work performed in support of MSD trials. MSD does not pay incentives to enroll participants in its trials. However, when enrollment is particularly challenging, additional payments may be made to compensate for the time spent in extra recruiting efforts.

MSD does not pay for participant referrals. However, MSD may compensate referring physicians for time spent on medical record review and medical evaluation to identify potentially eligible participants.

B. Clinical Research Funding

Informed consent forms will disclose that the trial is sponsored by MSD, and that the investigator or sponsoring institution is being paid or provided a grant for performing the trial. However, the local ethics committee may wish to alter the wording of the disclosure statement to be consistent with financial practices at that institution. As noted above, all publications resulting from MSD trials will indicate MSD as a source of funding.

C. Funding for Travel and Other Requests

Funding of travel by investigators and support staff (e.g., to scientific meetings, investigator meetings, etc.) will be consistent with local guidelines and practices.

V. Investigator Commitment

Investigators will be expected to review MSD's Code of Conduct as an appendix to the trial protocol, and in signing the protocol, agree to support these ethical and scientific standards.

